5. ANALYSES AND SUMMARIES

In general, observed values and change from baseline (where applicable) will be descriptively summarized by treatment group with number of observations, mean, SD, min, 1st, 2nd (median) and 3rd quartiles, and max, unless otherwise specified. For log-transformed values the geometric mean and 95% CI will be presented with the summary statistics.

Data will be summarized and analyzed by treatment group for the main population of interest and a separate sensitivity/supplementary analysis(ses) based on the chosen analysis set from Section 3).

Endpoint	Analysis Set Applied for Main Analysis	Analysis Set Applied for Sensitivity/Supplementary Analysis
Biopsy (Vh:Cd, IEL Density Marsh-Oberhuber Score)	Full Analysis Set	Per Protocol Set and Safety Analysis Set
Biomarker (IL2)	Biomarker Analysis Set	Per Protocol Set and Safety Analysis Set
PK	PK Analysis Set	N/A
PRO (CDS, PGIS, PGIC)	Full Analysis Set	N/A
Demography and Safety	Safety Analysis Set	N/A
ADA	Safety Analysis Set	N/A

5.1. Primary Endpoint Analysis: Vh:Cd

The primary endpoint is the change from baseline in Vh:Cd ratio as assessed by EGD with biopsy after 2-week GC (at Day 29).

Raw data will be descriptively summarized by treatment group with number of observations, mean, SD, min, 1st, 2nd and 3rd quartiles, and max for the FAS.

5.1.1. Main Analysis

The Hypothetical estimand, Estimand 1 (Section 1.1.1) will be addressed with the following analysis: change from baseline in Vh:Cd ratio at Day 29 will be analyzed using ANCOVA model (Section 4.2.1) for the FAS Population. The LSM change from baseline and associated 95% CI, LSM difference of the change from baseline between KAN-101 and PBO, 95% CI, and p-value will be presented along with summary statistics.

5.1.2. Sensitivity/Supplementary Analysis

Per-protocol (PP) additional sensitivity/supplementary analyses will be performed for change from baseline in Vh:Cd ratio at Day 29 visit using the same approach of main analysis as described above, 5.1.1 with the analysis sets stated in Section 5. Same analysis will be performed for SAS as well.

5.2. Secondary Endpoints

5.2.1. GC IL-2

GC IL-2 change from pre GC to post GC at Day 15 will be analyzed.

5.2.1.1. Main Analysis

Log transformed GC IL-2 change from pre GC to post GC at Day 15 will be analyzed using ANCOVA model as described in Section 4.2.1 based on Estimand 2 (see Section 1.1.2) for the BS. The LSM change (log transformed), LSM difference of LSM change (log transformed) between KAN-101 and PBO, 95% CI, and p-value will be presented. Exponentially transformed values for LSM, LSM difference, 95% CI will be presented as well.

5.2.1.2. Sensitivity/Supplementary Analysis

The above analysis will also be performed for the log transformed GC IL-2 for the analysis sets stated in Section 5 as a supplementary analysis.

5.2.2. IEL density in duodenum biopsy

Summary statistics will be provided for observed values for IEL and the change from baseline at Day 29.

5.2.2.1. Main Analysis

IEL change from baseline at Day 29 will be analyzed using ANCOVA model as described in Section 4.2.1 based on Estimand 3 (see Section 1.1.2) for the FAS. The LSM change, LSM difference of LSM change between KAN-101 and PBO, 95% CI, and p-value will be presented.

5.2.2.2. Sensitivity/Supplementary Analysis

The above analysis will be performed for PPS and the SAS as a sensitivity/supplementary analyses.

5.2.3. Incidence and Severity of TEAEs as Assessed by the CTCAE

See safety Section [5.5.1](#).

5.2.4. Incidence of Development of ADA During the Study

Participants positive for ADA (screening, confirmatory, specificity and titer) will be summarized by treatment group and timepoint with number and percent for the SAS.

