**Table 1. Schedule of Assessments**

Abbreviations used in this table may be found in Appendix 12 .	Scr.	Treatment Period				Gluten Challenge (Day 15 to 28)			Biopsy	FU	ET	Notes
Visit Identifier	V1	V2	V3	V4	V5	V6	V7	V8	V9	ET		
 
• Day relative to start of study intervention (Day 1).
 
• See Section 8.4.3 for follow-up AE and SAE assessments.
 
• D16 and D21 are phone call visits (See Section 8.1.1) for collection of AEs and concomitant medications.
 

Type (Site or Phone Call)	Site	Site	Site	Site	Site	Phone	Phone	Site	Site	Site		
Study Day (D)	Up to -42 days	D1	D4	D7	D15	D16	D21	D29	D42	ET		
Visit Window (days)					+2	±2	+3	+3				
ADA sample		X		X				X	X	X		
 
• D1 & D7 samples should be taken pre-dose (at least 5 minutes prior to infusion).
 

Plasma biomarker (includes IL-2) sample		X	X	X	X			X	X	X		
 
• See Section 8.2.2 for additional information.
 
• D1, D4, and D7 samples should be taken pre-dose (at least 5 minutes prior to infusion) and 4 hours post end of infusion ± 15 minutes. Day 15 sample should be collected prior to GC and at 4 hours (± 15 minutes) after GC.
 
• A single sample is collected on D29, D42, and ET.
 
• Participants who withdraw from treatment and do not receive 3 full doses should not have plasma samples collected at D15, D29, and D42.
 

ADA – Anti-Drug Antibody; AE – Adverse Event; CDS – Celiac Disease Symptom Diary; CeD – Celiac Disease; D – Day; DGP IgG – Deamidated Gliadin Peptide, Immunoglobulin G; ECG – Electrocardiogram; eDiary – Electronic Diary; EGD – Esophagogastroduodenoscopy; ET – Early Termination; FU – Follow Up; GC – Gluten Challenge; GFD – Gluten Free Diet; HBV – Hepatitis B Virus; HCV – Hepatitis C Virus; HIV – Human Immunodeficiency Virus; HLA – Human Leukocyte Antigens; IL-2 – Interleukin-2; IV – Intravenous; PGIC – Patient Global Impression of Change; PGIS – Patient Global Impression of Severity; PK – Pharmacokinetics; PRO – Patient Reported Outcome; SAE – Serious Adverse Event; Scr – Screening; tTG, IgA – Tissue Transglutaminase Immunoglobulin A; V – Visit

CONFIDENTIAL

CT02-GSOP Clinical Protocol Template Phase 1 2 3 4 (14 April 2023)

Page 26

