
 
Determine the effects of KAN-101 on histologic features (IELs density) in duodenum biopsies following 2-week GC.
 
	
 
Changes from baseline in IEL density in duodenum biopsy after 2-week GC (at Day 29)
 
	
Estimand 3 is the hypothetical estimand, which estimates the treatment effect of KAN-101 vs placebo for change from baseline in duodenal IEL density under the scenario of no intercurrent events. It includes the following 5 attributes:
 
 
Population: Participants who complete all 3 doses of study intervention and complete at least 7 days of GC.
 
Variable: IEL change from baseline at Day 29.
 
Treatment conditions: KAN-101 or placebo.
 
Intercurrent Events: Prohibited medication. All data collected after any intercurrent events will be excluded.
 
Population level summary: The LSM difference of the change from baseline in IEL between KAN-101 and placebo.
 

 
Assess the safety and tolerability of KAN-101 in participants with CeD.
 
	
 
Incidence and severity of treatment emergent AEs as assessed by the CTCAE v6.0 (or higher)
 
Incidence and titer of KAN-101 ADA.
 
	Not applicable. Not applicable.

 
Assess the PK of multiple doses of KAN-101 in participants with CeD.
 
	
 
Plasma concentration of KAN-101, and associated KAN-101 parameters: AUCinf, AUClast, Cmax, Tmax and t1/2
 
	Not applicable.
Tertiary/Exploratory:	Tertiary/Exploratory:	Tertiary/Exploratory:

 
Evaluate changes in histological features (Marsh-Oberhuber score) after a 2-week GC
 
	
 
Changes from baseline in Marsh-Oberhuber score assessed via EGD with biopsy after 2-week GC
 
	Not applicable.

Objectives	Endpoints	Estimands

Assess the impact of KAN-101 administration on the incidence of CeD symptoms before and during GC as measured using CDSD v2.1.

	

Changes from baseline in symptoms PROs including: CDSD v2.1, PGIC and PGIS over time.

	Not applicable.

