#### **Disease Characteristics:**

2. Previous diagnosis of CeD, based on documentation in the source data:
  - Positive celiac serology (eg, tissue transglutaminase IgA antibody and/or deamidated DGP IgG)
    - AND
  - Intestinal histology consistent with  $\geq$  Marsh Type II or with evidence of villous atrophy.
3. Have HLA-DQ2.5 genotype (HLA-DQA1\*05 and HLA-DQB1\*02) (homozygotes or heterozygotes).
4. Negative or weak positive for transglutaminase IgA AND negative or weak positive for DGP-IgA/IgG during screening.
5. Screening intestinal biopsy demonstrating Vh:Cd ratio of 2.3 or higher.

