1.1. Study Objectives, Endpoints, and Estimands

Study objectives, corresponding endpoints, and estimands are provided in the Table 2 below.

Table 2 Objectives, Endpoints, and Estimands

Objectives	Endpoints	Estimands
Primary:	Primary:	Primary:
Assess the ability of KAN-101 to attenuate GC-induced changes in duodenal histology as measured by changes in villus-height:crypt depth (Vh:Cd) ratio after a 2-week GC.	Changes from baseline in Vh:Cd ratio as assessed by esophagogastroduodenoscopy (EGD) with biopsy after 2-week GC (at Day 29).	Estimand 1: a hypothetical estimand (Section 1.1.1).
Secondary:	Secondary:	Secondary:
Examine the impact of KAN-101 on biomarker response (interleukin-2 [IL-2]) in peripheral blood following GC	IL-2 change from Day 15 (first day of GC) pre GC to Day 15 post GC.	Estimand 2: a hypothetical estimand (Section 1.1.2).
Determine the effects of KAN-101 on histologic features (intraepithelial lymphocytes [IELs] density) in duodenum biopsies following 2-week GC.	Changes from baseline in IEL density in duodenum biopsy after 2-week GC (at Day 29)	Estimand 3: a hypothetical estimand (Section 1.1.2).
Assess the safety and tolerability of KAN-101 in participants with CeD.	Incidence and severity of treatment emergent adverse events (TEAEs) as assessed by the Common Terminology Criteria for Adverse Events (CTCAE) v6.0 (or higher).	Not applicable.
	Incidence and titer of KAN-101 anti-drug antibodies (ADA).	Not applicable.
Assess the pharmacokinetics (PK) of multiple doses of KAN-101 in participants with CeD.	Plasma concentration of KAN-101, and associated KAN-101 parameters: AUC_{inf} , AUC_{last} , C_{max} , T_{max} and $t_{1/2}$	Not applicable.

Table 2 Objectives, Endpoints, and Estimands

Objectives	Endpoints	Estimands
Tertiary/Exploratory:	Tertiary/Exploratory:	Tertiary/Exploratory:
Evaluate changes in histological features (Marsh-Oberhuber score) after 2-week GC	Changes from baseline in Marsh-Oberhuber score after 2-week GC (at Day 29)	Not applicable.
Assess the impact of KAN-101 administration on the incidence of CeD symptoms before and during GC as measured using CDSD v2.1.	Changes from baseline in symptoms PROs including: CDSD v2.1, PGIC and PGIS over time.	Not applicable.
Assess whether KAN-101 affects the incidence and/or titer of post-GC celiac serology.	Change from baseline in incidence and titer of tTG IgA and DGP IgG at Day 42.	Not applicable.

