2.2. Secondary Endpoints

- GC IL-2 change from Day 15 (first day of GC) pre-GC to Day 15 post GC.

GC IL-2 will be log transformed prior to calculating the change.

- Change from baseline in IEL density in duodenum biopsy after 2-week GC (at Day 29).

The biopsy will be performed at screening and Day 29, or ET visit. The Baseline is the last non-missing IEL density at screening.

- Incidence and severity of TEAEs as assessed by the CTCAE.

See [Section 2.5.1](#).

- Incidence and titer of KAN-101 ADA.

Positive of ADA will be assessed at Days 1, 7, 29, 42 or early termination (ET) visit.

- Plasma concentration of KAN-101, and associated KAN-101 parameters: AUC_{inf}, AUC_{last}, C_{max}, T_{max} and t_{1/2}.

Parameter	Definition	Method of Determination
AUC _{last}	Area under the plasma concentration-time profile from time 0 to the time of the last quantifiable concentration (C _{last})	Linear/Log trapezoidal method
AUC _{inf}	Area under the plasma concentration-time profile from time 0 extrapolated to infinite time	AUC _{last} + (C _{last} /K _{el}), where C _{last} is the predicted plasma concentration at the last quantifiable time point estimated from the log-linear regression analysis
C _{max}	Maximum plasma concentration	Observed directly from data
T _{max}	Time to first occurrence of C _{max}	Observed directly from data.
t _{1/2} ^a	Terminal elimination half-life	Log _e (2)/K _{el} , where K _{el} is the terminal Phase rate constant calculated by a linear regression of the loglinear - concentration time- curve. Only those data points judged to describe the terminal log-linear decline will be used in the regression

- a. If data permits.

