Appendix 2. Data Derivation Details

Appendix 2.1. Definition and Use of Analysis Windows in Reporting

Analysis windows will be used for PROs and vital signs, and laboratory tests.

If more than one observation from the same participant falls into the same analysis window, the value closest to the targeted day will be used as the observation for that visit. All observations will, however, be included in the listings.

Table 3 Analysis Windows for PGIS and PGIC

Visit Label	Targeted Day	Analysis window for data sets
Baseline (Screening up to first dosing date)	Day 1	Last observation up to and including first dosing date
Day 15	Day 15	After last dose – First day of GC
Day 29	Day 29	Second day of GC – Day 35
Day 42	Day 42	Day 36 – end of study

Table 4 Analysis Windows for Vital Signs

Visit Label	Targeted Day	Analysis window for data sets
Baseline (Screening up to first dosing date)	Day 1	Last observation up to first dosing
Day 1 during dosing	Day 1 during dosing	Start of Day 1 dosing to end of Day 1 dosing
Day 1 after dosing	Day 1 after dosing	End of Day 1 dosing to end of Day 1
Day 4 before dosing	Day 4 pre-dosing	Day 2 - Day 4 pre-dosing
Day 4 during dosing	Day 4 during dosing	Day 4 start of dosing - Day 4 end of dosing
Day 4 after dosing	Day 4 after dosing	Day 4 end of dosing - end of Day 4
Day 7 before dosing	Day 7 pre-dosing	Day 5 - Day 7 pre-dosing
Day 7 during dosing	Day 7 pre-dosing	Day 7 start of dosing - Day 7 end of dosing
Day 7 after dosing	Day 7 after dosing	Day 7 end of dosing - end of Day 7
Day 15	Day 15 pre-GC	Day 8 - pre-GC of first GC day
Day 29	Day 29	After GC of first GC day – Day 35
Day 42	Day 42	Day 36 – end of study

Table 5 Analysis Windows for Laboratory Tests

Visit Label	Targeted Day	Analysis window for data sets
Baseline (Screening up to first dosing date)	Day 1	Last observation up to first dosing
Day 4	Day 4 pre-dosing	Day 1 after dosing - Day 4 pre-dosing
Day 7	Day 7 pre-dosing	Day 4 after dosing - Day 7 pre-dosing
Day 15	Day 15 pre-GC	Day 7 after dosing - pre-GC of first GC day
Day 29	Day 29	post-GC of first GC day – Day 35
Day 42	Day 42	Day 36 – end of study

Table 6 Analysis Windows for ADA

Visit Label	Targeted Day	Analysis window for data sets
Baseline (Screening up to first dosing)	Day 1 pre-dosing	Last observation prior to first dosing date
Day 7	Day 7 pre-dosing	Day 2 - Day 7 pre-dosing
Day 29	Day 29	Day 8 – Day 35
Day 42	Day 42	Day 36 – end of study

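### SAP 5.2.4 is titled as incidence of ADA development but plans only the percent positive at each visit, which is not incidence

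*SAP*

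**What the plan says.** Protocol section 3 lists "Incidence and titer of KAN-101 ADA" as a secondary endpoint, and SAP 1.1 and 2.2 repeat it. On timing, SAP 2.2 says "Positive of ADA will be assessed at Days 1, 7, 29, 42 or early termination (ET) visit". Protocol Table 1 shows that the Day 1 and Day 7 samples are drawn before that day's infusion, so Day 1 is the only scheduled sample taken before any treatment.

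The analysis section, SAP 5.2.4, is headed "Incidence of Development of ADA During the Study". Its whole content is: "Participants positive for ADA (screening, confirmatory, specificity and titer) will be summarized by treatment group and timepoint with number and percent for the SAS". SAP Appendix 2.1, Table 6, sets a baseline window and Day 7, Day 29 and Day 42 windows for ADA. The baseline value is the "Last observation prior to first dosing date".

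**The concern.** Incidence means new cases among people who could become cases. The rule counts everyone positive at a given visit, whatever their status before dosing, and gives no total across visits. A participant positive on Day 1 with an unchanged result afterwards is counted at every post-dose visit although nothing developed. Two participants who start negative, one positive only at Day 29 and the other only at Day 42, appear once each in separate rows and are never reported as two participants who developed ADA. The rule also does not identify a titer rise in someone already positive at baseline.

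At stake is whether a named secondary safety endpoint has a prespecified analysis. Pre-dose positives are at least conceivable here. KAN-101 contains a gliadin peptide (Protocol 2.2.2), and the inclusion criteria admit participants who are "Negative or weak positive for transglutaminase IgA AND negative or weak positive for DGP-IgA/IgG during screening". Whether such antibodies react in the ADA assay is not stated and would be an assumption. The point does not depend on it.

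**Working it through.** The documents state no ADA rate or ADA-based sample size, so there is no figure to reproduce. The check is whether any other text supplies the missing rule, followed by simple counts.

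**1. Is the rule elsewhere?**
- Protocol 9.4.3.3 refers to 9.4.6, which is descriptive only. Protocol 9.4.7 adds only that immunogenicity is described.
- SAP Table 6 defines a baseline visit for ADA, but no text uses it to classify later positives.
- SAP Appendix 1 has no ADA row, and SAP section 7 does not mention ADA.
- SAP 2.5.1 does give a treatment-emergent rule, but for adverse events only.

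Neither document defines treatment-induced or treatment-boosted ADA, an any-time post-dose count, or a baseline-negative denominator.

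**2. Counts under the written rule.** Inputs: n = 26 per arm (SAP 1.3), and three scheduled post-dose visits at Days 7, 29 and 42 (SAP 2.2). Assumed: all samples available; b participants positive on Day 1 and at every later visit; t different participants newly positive at each post-dose visit and at that visit only.

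- Shown at each post-dose visit = (b + t)/26
- New among baseline negatives = 3t/(26 − b)

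| b | t | Shown per visit | New, cumulative |
|---|---|---|---|
| 3 | 0 | 3/26 = 11.5% | 0/23 = 0% |
| 0 | 2 | 2/26 = 7.7% | 6/26 = 23.1% |
| 3 | 2 | 5/26 = 19.2% | 6/23 = 26.1% |

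Over b = 0 to 5 and t = 0 to 3, the per-visit figure runs from 0% to 8/26 = 30.8%, and the cumulative new figure from 0% to 9/21 = 42.9%.

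**3. Does the table determine incidence?** Take no baseline positives and counts of 2, 2, 2 at the three visits. If the same two people are positive throughout, 2/26 = 7.7% ever developed ADA. If they are six different people, it is 6/26 = 23.1%. The same table fits both.

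**4. If new positives persist.** Take b = 0, with two new positives arising before each visit and remaining positive. The counts are 2, 4 and 6, and the Day 42 row reads 6/26 = 23.1%, which equals the cumulative incidence. The understatement therefore arises only from transient positives or missing later samples.

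**5. Baseline window.** Table 6 targets Day 1 pre-dosing, but its window closes before the first dosing date, and the Day 7 window opens on Day 2. Read literally, the scheduled Day 1 pre-dose sample falls in neither. The vital-sign and laboratory windows (Tables 4 and 5) run up to first dosing and do not have this problem.

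**The case against.** The strongest case against is that little is lost in practice.

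- **Recoverability.** A reader might infer that incidence can never be recovered. That is true of the summary table alone. SAP 5.5 plans participant listings for safety endpoints, and Appendix 2.1 keeps all observations in listings, so with about 52 participants incidence can be derived later. What remains is that the definition and any titer threshold would then be chosen with the results in view.
- **False drug signal.** A reader might infer that pre-dose antibodies would pass as a drug effect. Baseline has its own row and there is a randomised placebo column, so they would be visible. This stands as mitigation, but neither feature identifies which post-dose positives are new.
- **Titer.** A reader might infer that titer gets no summary. The default in SAP section 5 (descriptive statistics of observed values and change from baseline unless otherwise specified) may cover it. Whether 5.2.4 overrides that default is unclear, so only an explicit statement is needed.
- **Wording.** The endpoint says incidence, and development appears only in the 5.2.4 heading. But even if incidence is read loosely as ever positive, by-visit counts do not give it.
- **Sponsor standards.** SAP 5.5 refers to them, and they might contain a rule. SAP 5.2.4 does not cite them.

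**Conclusion.** The point holds as a gap between endpoint and analysis: the plan yields visit-wise prevalence where the endpoint is incidence. That follows from the text and needs no assumption about ADA rates.

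The size is unknown. The percentages above rest on assumed counts, complete sampling and, for the understatement, new positives that are transient and in different people. With persistent new ADA, the Day 42 row is not too low. The documents do not support a claim that the planned table must be wrong in a particular direction, or that weakly positive celiac serology will produce baseline ADA positives.

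The consequence is minor. ADA is a descriptive secondary safety endpoint in a Phase 2a trial, with no test or decision rule attached in these documents. The primary analysis, its power and its alpha are untouched.

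**What to change.** In SAP 5.2.4:

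- Define treatment-emergent ADA as either treatment-induced (baseline negative with any later confirmed positive) or treatment-boosted (baseline positive with a titer rise by a factor fixed in advance from the assay's performance).
- Report cumulative n/N by arm over all post-dose samples, including ET, among SAS participants with a baseline and at least one post-dose result. Use baseline negatives as the denominator for the treatment-induced part.
- Report baseline prevalence separately by arm.
- State that titer is summarised among confirmed positives.
- Keep the by-visit table as supportive.

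In SAP Appendix 2.1, Table 6, change the end of the ADA baseline window from the first dosing date to the first dose, so that the Day 1 pre-dose sample counts as baseline.

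The cost is SAP wording and one additional table. Every sample needed is already scheduled.

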5.2.5. PK Concentration

PK concentration will be descriptively summarized by treatment group and nominal timepoints with number of observations, mean, SD, min, 1st, 2nd and 3rd quartiles, max for PKAS. Line plot will be provided by treatment group for mean (+/-SD) concentration-time profiles using linear and semi-log scale

5.2.6. PK Parameters

PK parameters listed in [Section 2.2](#) (AUC_{inf}, AUC_{last}, C_{max}, T_{max}, and t_{1/2}) will be descriptively summarized by treatment group with number of observations, mean, SD, min, 1st, 2nd and 3rd quartiles, max, GM, and %CV for PKAS. No GM and %CV for T_{max}.

5.3. Tertiary/Exploratory

5.3.1. Change from baseline in Marsh-Oberhuber score at Day 29

Marsh-Oberhuber score at baseline and Day 29 observed values will be summarized with number of observations, frequency and percentage for each category. The shift from baseline to Day 29 will be summarized as well. The analysis sets used for this endpoint is found in Section [5](#).

5.3.2. CDSD

The weekly average score of each severity item and frequency question of CDSD (Diarrhea, Abdominal Pain, Bloating, Nausea, Number of times Vomiting, Tiredness, Number of Bowel Movements and Number of events of Diarrhea) as well as the weekly average CDSD Total Score, weekly average CDSD GI Domain Score (see [Section 2.3](#) and [Appendix 2.2](#)) and change from baseline will be descriptively summarized as stated in Section 5 for each treatment group by timepoint.

The change from baseline for weekly average of each of the 5 severity items and 3 frequency questions, the weekly average CDSD Total Score, and the weekly average CDSD GI Domain Score will be analyzed using ANCOVA models in [Section 4.2.1](#) by timepoint. LSM of the treatments with 95% CI, LSM of the treatment difference with PBO, p-value and 95% CI will be generated.

If there are multiple records on a same day, the earliest one will be used for analysis.

The analysis set(s) used for these endpoints are found in Section [5](#).

Weekly Time Definitions:

	Regardless the day of Day 15 GC	Day 15 GC is at day 14	Day 15 GC is at day 15	Day 15 GC is at day 16	Day 15 GC is at day 17
Baseline	Day -7 to -1				
Week 1	Day 1 to 7				
Week 2		Day 8 to 13	Day 8 to 14	Day 8 to 15	Day 8 to 16
Week 3		Day 14 to 21	Day 15 to 21	Day 16 to 21	Day 17 to 21
Week 4	Day 22 to 28				
Week 5	Day 29 to 35				
Week 6	Day 36 to 42				

In addition, the change from baseline in CDSD Nausea score and vomiting frequency for Day 15, 3-day average and 7-day average (weekly average) score, will be summarized as stated above, and analyzed within placebo and KAN treatment, evaluating the paired difference from baseline using the Wilcoxon Signed-rank test. The Mann-Whitney U test (Wilcoxon Rank Sum test) will be used to test the difference in the change from baseline for placebo vs KAN-101. The median difference between treatment groups estimated by the Hodges–Lehmann method along with the 95% CI will be reported as well.

Line plots by treatment group will be provided for LSM 95% CI).

